### **5.5.8 Drug Accountability**

Upon receipt of a shipment of veliparib, the representative at each site will verify that study drug supplies are received intact and in the correct amounts. This will be documented by signing and dating the Proof of Receipt (PoR) or similar document respectively via direct recording in the IRT. The shipment receipt must be acknowledged in the IRT in order to become available for dispensation to subjects. All veliparib/placebo must be retained in the designated secure area under proper storage conditions. The study site will record the kit number of veliparib/placebo given to each subject in the source documents and on the eCRF.

The IRT will maintain a current and accurate inventory of study drug, accountability, reconciliation, returns, and destruction for each site. The IRT will also include the lot number, the bottle/kit numbers, and the date veliparib/placebo was dispensed for each subject.

In the event the IRT is not operable, the above information will be documented on forms provided/approved by the Sponsor.

The Investigator or designee will document the bottles of veliparib/placebo returned and the number of capsules on the appropriate form in the IRT. If the number of capsules taken and the number of capsules returned do not add up to the number of capsules dispensed, an explanation is required and should be documented in the IRT.

An overall accountability of the study drug will be performed and verified by the AbbVie monitor throughout the study and at the site close-out visit. All study drug unit doses must be inventoried, accounted for, and returned to the destruction facility or to AbbVie or destroyed per instructions from AbbVie and according to local regulations.

The investigator and/or named the sub-investigators agree not to supply study medication to any persons not enrolled in the study.

The site will record the dose of carboplatin and etoposide given to each subject in the source documents and on the eCRF. As the investigator will obtain both carboplatin and etoposide commercially, site inventory and accountability of carboplatin and etoposide will not be performed, and drug accountability for carboplatin and etoposide will not be performed in the IRT. However, each site will be responsible for tracking the lot numbers for all carboplatin and etoposide dispensed.

## **5.6 Discussion and Justification of Study Design**

### **5.6.1 Discussion of Study Design and Choice of Control Groups**

The carboplatin and etoposide combination chemotherapy is standard first-line treatment for ED SCLC. Veliparib may have a potential benefit for subjects with ED SCLC. This Phase 1 dose escalation/Phase 2 randomized double-blind study will determine the recommended Phase 2 dose of veliparib in combination with carboplatin and etoposide (Phase 1 portion), and will evaluate the treatment effect due to the addition of veliparib to carboplatin/etoposide chemotherapy followed by veliparib monotherapy maintenance in subjects with ED SCLC (Phase 2 portion).

### **5.6.2 Appropriateness of Measurements**

The Phase 1 dose escalation portion of the study is a standard 3 + 3 design. Standard pharmacokinetic, statistical, clinical, and laboratory procedures will be utilized in this study.

The randomized double-blind Phase 2 portion will utilize a well-established surrogate ED SCLC and other solid tumor endpoint of progression free survival using RECIST 1.1 as a guideline for the measurement of responses in subjects with advanced or metastatic solid tumors. Secondary and tertiary endpoints of objective response rate, duration of overall response and overall survival of subjects receiving veliparib maintenance monotherapy will also be evaluated.

### **5.6.3 Suitability of Subject Population**

Subjects with ED SCLC and advanced/metastatic solid tumors (Phase 1) and with treatment-naïve ED SCLC (Phase 2) and meeting inclusion and exclusion selection criteria as outlined in the Section 5.2.1 and Section 5.2.2 are appropriate for this study. Subjects with advanced/metastatic solid tumors will allow defining the recommended Phase 2 dose as the tolerability of the study regimen in this population should be similar to the target population with ED-SCLC. Subjects with treatment-naïve ED SCLC are appropriate to define efficacy and safety of the study regimen since carboplatin/etoposide is the first line standard of care in this tumor type and SCLC is the intended indication for further clinical evaluation of veliparib/carboplatin/etoposide combination.

### **5.6.4 Selection of Doses in the Study**

#### **Phase 1 Dose Escalation**

The initial starting dose of 80 mg BID veliparib in the Phase 1 portion of the study was derived from the results obtained in the ECOG E2511, GOG 9923 and AbbVie M10-898 clinical studies, as well as from the non-clinical studies.

Doses for carboplatin in combination with etoposide will be given as per standard of care in first line treatment for extensive stage SCLC as per NCCN guideline 2014.

The dose for veliparib monotherapy is 400 mg BID. This dose is well characterized for safety and tolerability based on the experience from multiple clinical trials.

#### **Phase 2 Randomized Double-Blind**

The RPTD has been defined in the Phase 1 portion of the study as veliparib 240 mg BID administered on Days -2 – 12 (14-Day schedule), carboplatin AUC 5 mg/ml\*hr administered on Day 1, etoposide 100 mg/m^2 administered on Days 1 – 3 of 21-Day cycles.

The dose for veliparib/placebo monotherapy is 400 mg BID administered continuously in 21-Day cycles.

## 5.7 Dose Reductions or Delays

If a subject experiences an adverse event that results in a delay in starting a cycle or requires that study regimen is delayed or interrupted during a cycle, the subject will complete the planned activities per Section 5.7.1 until resuming treatment.

Study drug interruptions for events that are clearly not related to the study drug treatment, (e.g., underlying cancer, planned surgical procedures or acute viral illnesses), should not necessitate a dose reduction. The timing of dose resumption should be at the discretion of the Investigator. Study treatment may be delayed for up to 21 days due to toxicity. Toxicity-related delays greater than 21 days will result in study treatment discontinuation.

**Table 16. Guidelines for Veliparib, Carboplatin, and Etoposide Dose Reduction Levels During Combination Therapy**

Dose Reductions	Carboplatin	Etoposide a	Veliparib b
Starting Dose	AUC 5	100 mg/m 	Phase 1: As assigned Phase 2: 240 mg BID
Dose Reduction 1	AUC 4	75 mg/m 	Phase 1: Next lower DL (assigned –1) Phase 2: 200 mg BID
Dose Reduction 2	No Additional Reductions Allowed	55 mg/m 	Phase 1: Next lower DL (assigned –2) Phase 2: 160 BID

a. Refer to Section 5.7.2.1.2 for etoposide dose reduction guidelines related to bilirubin.

b. Refer to Section 5.7.1 for veliparib dose reduction guidelines for maintenance therapy. "Next lower DL" refers to the daily dose levels tested in the dose escalation part of the study. The dose of each drug can be reduced independently based on the observed toxicities. For veliparib dose level of 80 mg (Phase 1 only), Dose Reduction 1 is to 60 mg, Dose Reduction 2 is to 40 mg.

### 5.7.1 Veliparib/Placebo Dose Reductions and Interruptions

The following are guidelines for dose reduction, interruption and discontinuation of veliparib/placebo during combination therapy:

1. Veliparib/placebo will be discontinued if both carboplatin and etoposide are discontinued prior to the completion of the planned number of combination therapy cycles.
2. For any subject who experiences Grade 3/4 toxicity which is not attributable to carboplatin/etoposide or the underlying disease, refer to [Table 17](#) for dosing guidelines.
3. Two dose reductions are prospectively allowed during combination therapy for subjects who experience toxicity attributable to veliparib/placebo. Refer to [Table 16](#) for dose reduction guidelines.
  - a. Veliparib dose reduction at C1D1 is allowed in case of nausea and vomiting attributable to C1D-2 and C1D-1 veliparib doses
  - b. All veliparib/placebo dose reductions within combination therapy cycles are permanent.
  - c. If further dose reductions (beyond prospectively allowed two) are required, sites must contact the AbbVie TA MD.
4. Any  $\geq$  Grade 2 event of seizure attributed to veliparib/placebo requires discontinuation of veliparib/placebo.
5. Veliparib/placebo interruptions will not affect the schedule of planned study procedures and will not be replaced. If veliparib/placebo-related toxicity necessitates the delay in veliparib/placebo re-initiation beyond the scheduled start of the next combination therapy cycle, the start of the cycle should be delayed until veliparib/placebo can be restarted. The AbbVie TA MD may be contacted ([Section 6.6](#)) for subjects who require more than a 2-week delay in the re-initiation of the next cycle.

The following are guidelines for dose reduction, interruption and discontinuation of veliparib/placebo during Maintenance Therapy:

1. Dose Reduction 1: 300 mg BID.

2. Dose Reduction 2: 200 mg BID.
3. Subjects requiring dose reduction of veliparib/placebo to below 200 mg BID will be discontinued from treatment.
4. For subjects who experience any Grade 3/4 toxicity during maintenance therapy which is attributable to veliparib, refer to [Table 18](#) for dosing guidelines.

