- i. Tumor assessment and assessment of response will occur every 6 weeks ( $\pm$  1 week) from CID-2 for the first 30 weeks, then every 9 weeks ( $\pm$  1 week) thereafter. A tumor assessment will be performed at the Final Visit for subjects who discontinue the study for reasons other than radiographic progression and if no assessment has been performed within the last 4 weeks. An unscheduled assessment should be obtained in such subjects if a Final Visit will not be conducted. Subjects in Post-Treatment Follow-Up should continue to receive tumor assessments at the protocol defined time points until an event of radiographic progression.
- j. Veliparib will be dosed orally at 240 mg BID and 14-day schedule for up to 6 cycles. Veliparib will be administered after the pre medications on all days when given with chemotherapy. Veliparib will be given approximately every 12 hours with a glass of water (approximately 240 mL).
- k. Pre-medication will be given as per institutional guidelines.
- l. Starting at Maintenance Day 1 and all subsequent monotherapy cycles, veliparib or placebo will be dosed orally at 400 mg BID and continuous (21-day) dosing schedule. Subjects should remain on veliparib until disease progression or unacceptable toxicity occurs.

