## **5.4 Removal of Subjects from Therapy or Assessment**

### **5.4.1 Discontinuation of Individual Subjects**

Each subject has the right to withdraw from the study at any time. In addition, the investigator may discontinue a subject from the study at any time if the investigator considers it necessary for any reason, including the occurrence of an adverse event or noncompliance with the protocol. Subjects who withdraw or are discontinued from the study will not be replaced except as described in Section 5.1, unless it is mutually agreed upon, in writing, by the investigator and AbbVie.

When a subject discontinuation from the study (without reaching a protocol-defined endpoint) is planned, the Investigator is to notify the AbbVie TA MD or the clinical team representative (Section 7.0) via telephone as soon as possible (provided, in each case, subject care and safety are not compromised). If not notified prior to discontinuation, the AbbVie TA MD may contact the site to discuss the reason for withdrawal from the study.

If a subject is discontinued from the study with an ongoing adverse event or an unresolved laboratory result that is significantly outside of the reference range, the investigator will attempt to provide follow-up until a satisfactory clinical resolution of the laboratory result or adverse event is achieved.

In the event that a positive result is obtained on a pregnancy test for a subject or a subject reports becoming pregnant during the study, the administration of study drug to that subject must be discontinued immediately. The investigator must report a pregnancy within 1 working day of the site being aware to one of the AbbVie representatives listed in Section 6.6 or Section 7.0.

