### **5.5 Treatments**

#### **5.5.1 Treatments Administered**

Phase 1 subjects will receive the following:

- Designated doses of veliparib BID on Days –2 through 5 or Day –2 through 12 (14-day schedule) or Day –2 to 19 (continuous schedule) + Carboplatin AUC

5 mg/mL\*min administered on Day 1 and Etoposide 100 mg/m^2 administered on Days 1 through 3 of each 21-day cycle for up to 4 cycles.

- Exception: Phase 1 subjects receiving non-continuous veliparib will have their Cycle 2 dosing schedule altered as follows to allow for the evaluation of veliparib effect on etoposide exposure: veliparib BID on Days 2 through 5 or Days 2 through 12 + Carboplatin AUC 5 mg/mL\*min administered on Day 1 and Etoposide 100 mg/m^2 administered on Days 1 through 3 of a 21-day cycle.
- Phase 1 subjects with SD, PR or CR at the completion of all scheduled combination therapy cycles will receive veliparib (400 mg) monotherapy, BID continuously in 21-day cycles starting on Day 1 of each cycle starting at Cycle 5.

Phase 2 subjects will receive the following:

- Veliparib/Placebo 240 mg BID on Day -2 through 12 (14-day schedule) + Carboplatin AUC 5 mg/mL\*min administered on Day 1 and Etoposide 100 mg/m^2 administered on Days 1 through 3 of each 21-day cycle for up to 6 cycles.
- Phase 2 subjects with SD, PR or CR at the completion of combination therapy cycles will receive veliparib (400 mg) or placebo monotherapy, BID continuously in 21-day cycles starting on Maintenance Day 1 of each cycle.

The sequence of administration is as follows on days when veliparib is dosed in combination with chemotherapy as described in [Figure 3](#):

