**Table 17. Dose Interruption or Reduction Due to Toxicity Attributable to Veliparib in the Combination Therapy Cycles**

Adverse Event	Veliparib
Any Grade 3 or 4 toxicity attributable to veliparib which is not attributable to carboplatin/etoposide or underlying disease	
 
1. Interrupt dosing in the current cycle until Grade 1 (or Grade 2 if present at baseline) and
 
2. Reduce veliparib dose to next lower dose level upon dosing re-initiation
 

**Table 18. Veliparib Dose Interruption or Reduction Due to Toxicity Attributable to Veliparib in the Maintenance Therapy Cycles**

Adverse Event	Veliparib
Any Grade 3 or 4 toxicity attributable to veliparib	
 
1. Interrupt dosing in the current cycle until Grade 1 (or Grade 2 if present at baseline) and
 
2. At resumption reduce veliparib dose to next lower monotherapy dose level
 

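### The mandatory stop for a veliparib-attributed seizure is written only for combination therapy; in maintenance, at a higher daily dose, Table 18 read literally permits resumption at 300 mg BID

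*Protocol*

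**What the plan says.** Section 5.7.1 of the protocol opens its first list of five items with "The following are guidelines for dose reduction, interruption and discontinuation of veliparib/placebo during combination therapy". Item 4 of that list is the only seizure dosing rule in either current document: ≥ "Grade 2 event of seizure attributed to veliparib/placebo requires discontinuation of veliparib/placebo".

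A second list follows, headed "guidelines for dose reduction, interruption and discontinuation of veliparib/placebo during Maintenance Therapy". It has four items: a first reduction to 300 mg BID, a second to 200 mg BID, a stop if a dose below 200 mg BID would be needed, and a referral to Table 18: "For subjects who experience any Grade 3/4 toxicity during maintenance therapy which is attributable to veliparib". None mentions seizure.

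Table 18 covers any attributable Grade 3 or 4 toxicity. Dosing is interrupted until Grade 1 (or Grade 2 if that was the baseline grade), and then: "At resumption reduce veliparib dose to next lower monotherapy dose level". It has no seizure exception.

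The maintenance rules also reach Phase 1, because under Section 5.5.1 "Phase 1 subjects with SD, PR or CR at the completion of all scheduled combination therapy cycles will receive veliparib (400 mg) monotherapy".

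**The concern.** Combination therapy has its own generic interrupt-and-reduce rule for Grade 3/4 toxicity (Table 17), and the protocol still adds item 4. It therefore treats interrupt-and-reduce as insufficient for a seizure. Maintenance has the parallel generic rule without the override, and it runs at the higher daily dose.

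The protocol treats seizure as a risk worth guarding against. Section 3.3.1 reports convulsions in animals and describes the nonclinical findings as related to dose. Sections 3.3.3 and 3.7 name seizure as a potential risk, though one not confirmed clinically. Exclusion criterion 6 removes subjects with a recent seizure or a neurological condition that raises seizure risk. No reason is given for a looser rule in maintenance.

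The consequence is a safety matter, not an efficacy one. Because the heading and the wording of item 4 point in different directions, two of the roughly 65 planned sites could handle the same blinded event differently. One of them could re-expose a subject after an attributed Grade 3/4 seizure and still be following the protocol.

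**Working it through.** There is no planned statistic to reproduce. The check has three parts: what each list requires, the dose comparison, and how many subjects could be affected.

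**1. The two periods side by side (Section 5.7.1, Tables 17 and 18)**

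| Event attributed to veliparib/placebo | Combination | Maintenance |
|---|---|---|
| Grade 2 seizure | Stop (item 4) | No stated action: Table 18 starts at Grade 3 |
| Grade 3/4 seizure | Stop (item 4, over Table 17) | Table 18: interrupt until recovery; any resumption is one level lower |

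Following Table 18 for a Grade 3/4 seizure, a subject at 400 mg BID may resume at 300 mg BID, and a subject already at 300 mg BID may resume at 200 mg BID. The list's only mandatory stop comes when a dose below 200 mg BID is needed. Elsewhere the protocol mentions seizures or convulsions only in the eligibility criteria, the risk and nonclinical statements, and the serious adverse event examples. None of these sets a dose action in maintenance.

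**2. Daily doses on dosing days**

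- Phase 2 combination levels (Table 16): 240 × 2 = 480; 200 × 2 = 400; 160 × 2 = 320 mg/day.
- Maintenance levels (Section 5.7.1): 400 × 2 = 800; 300 × 2 = 600; 200 × 2 = 400 mg/day.
- Starting doses, maintenance to combination: 800/480 = 1.67.
- First resumption level against each combination level where stopping is mandatory: 600/480 = 1.25; 600/400 = 1.50; 600/320 = 1.88.
- Lowest maintenance level against lowest combination level: 400/320 = 1.25.

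Daily dose is the relevant comparison because Section 3.3.2 reports minimal accumulation on BID dosing; cumulative dose per cycle is not used.

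**3. Subjects exposed to the gap**

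The ceiling on active maintenance is Arm A (about 60) plus Phase 1 (about 35): 60 + 35 = 95. The real number is lower, since maintenance requires completing combination therapy without progression. Placebo subjects in Arms B and C fall under the same blinded text but are not at drug risk in maintenance.

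The documents give no seizure rate. Assuming that 0.1% to 1% of subjects have an attributed Grade 2 or higher seizure in maintenance: 95 × 0.001 = 0.095 and 95 × 0.01 = 0.95, so about 0.1 to 1 subject.

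**The case against.** The strongest counter-argument is that item 4 carries no time limit in its own words. Items 1, 3 and 5 of the same list each refer to combination therapy or its cycles; item 4 does not. Item 4 already overrides Table 17, which has no seizure exception either, so a careful site might read Table 18 the same way. This stands as a possible reading. The heading above the list and the silence of the parallel maintenance list point the other way, and that ambiguity is the defect.

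Second, Table 18 does not order resumption; it fixes the dose if treatment resumes. That is correct, and the point here is only that resumption is permitted.

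Third, general safeguards cover maintenance. Table 8 states "Subjects should remain on veliparib until disease progression or unacceptable toxicity occurs", and under Section 5.4.1 "the investigator may discontinue a subject from the study at any time if the investigator considers it necessary for any reason". Section 5.7 ends treatment after a toxicity delay of more than 21 days. A convulsion is among the examples of important medical events in Section 6.1.4, reportable within 24 hours, and the sponsor's team monitors serious events as they are reported (Section 5.3.4). These make a careless rechallenge unlikely. None requires a stop for seizure, and the 21-day limit does not apply if the event resolves sooner. Such general safeguards also operate in combination, where the protocol still judged a mandatory stop necessary.

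Fourth, the event is rare. Seizure was unconfirmed clinically after about 3,700 exposed patients (Section 3.3.3), 400 mg BID is described as well characterized (Section 5.6.4), and subjects with CNS metastases are excluded. This is accepted. The dose ratios show that the rules are out of order; they do not measure a difference in risk.

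**Conclusion.** The concern holds and should be fixed. Section 5.7.1 states no seizure rule for maintenance. Followed literally, it permits resumption at 600 mg/day after an attributed Grade 3/4 seizure, while requiring a stop at 480, 400 and 320 mg/day in combination. It also leaves a Grade 2 seizure in maintenance without a stated action.

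Confidence in the reading of the text is high. The expected number affected is small: about 0.1 to 1 of at most 95 subjects, on an assumed rate of 0.1% to 1% that the documents neither support nor contradict. No endpoint, analysis or sample size depends on it. The weight comes from the seriousness of a named risk and from the protocol's own judgement, at lower doses, that stopping should be mandatory.

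**What to change.** Repeat item 4 in the maintenance list, or move it to a statement covering both periods, so that any Grade 2 or higher seizure attributed to veliparib/placebo ends veliparib/placebo at any point in treatment. Add a seizure exception to Table 18 that points to Section 5.7.1. The same note on Table 17 would be redundant but harmless.

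As context for intent only, and not as an error, the superseded text in Appendix G held the seizure item in one list together with the 300 and 200 mg BID monotherapy levels. If the sponsor's medical and safety team wants a different rule for maintenance, the protocol should state it and give the reason.

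The cost is one sentence and a table note, by amendment or safety letter, with no new procedures, data or patients. The downside is that a rare subject with an attributed seizure stops maintenance instead of continuing at a lower dose.

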**Table 17. Dose Interruption or Reduction Due to Toxicity Attributable to Veliparib in the Combination Therapy Cycles**

Adverse Event	Veliparib
Any Grade 3 or 4 toxicity attributable to veliparib which is not attributable to carboplatin/etoposide or underlying disease	
 
1. Interrupt dosing in the current cycle until Grade 1 (or Grade 2 if present at baseline) and
 
2. Reduce veliparib dose to next lower dose level upon dosing re-initiation
 

**Table 18. Veliparib Dose Interruption or Reduction Due to Toxicity Attributable to Veliparib in the Maintenance Therapy Cycles**

Adverse Event	Veliparib
Any Grade 3 or 4 toxicity attributable to veliparib	
 
1. Interrupt dosing in the current cycle until Grade 1 (or Grade 2 if present at baseline) and
 
2. At resumption reduce veliparib dose to next lower monotherapy dose level
 

